7.7.2 DIEPSS

1. Mean change in DIEPSS total score (excluding overall severity) from baseline to Week 6
2. Mean change in individual DIEPSS scores from baseline to Week 6
3. Mean change in DIEPSS total score (excluding overall severity) from the last evaluation before the initial application of DSP-5423P at each visit
4. Mean change in individual DIEPSS scores from the last evaluation before the initial application of DSP-5423P at each visit

The variables (1) will be analyzed using MMRM and the LOCF ANCOVA methods described above for the primary efficacy variable for the safety population. Summary statistics for the safety variables (1), and (2), will be provided by visit including LOCF endpoint by treatment group for the safety population. (3) and (4) will be provided for DSP-5423P dosed population.

7.7.3 C-SSRS

The number and percentage of subjects with any suicidal ideation and behavior will also be summarized. In addition, the total number and percentage of subjects with each type of suicidal ideation (i.e. 'Wish to be Dead', 'Non-Specific Active Suicidal Thoughts', 'Active Suicidal Ideation with Any Methods (Not Plan) without Intent to Act', 'Active Suicidal Ideation with Some Intent to Act, without Specific Plan', and 'Active Suicidal Ideation with Specific Plan and Intent') and suicidal behavior (i.e. actual attempts, interrupted attempts, aborted attempts, and preparatory acts or behavior) will be presented at baseline and each post-baseline visit for the double-blind treatment phase and the DSP-5423P treatment period. Note that for the DSP-5423P treatment period summary, baseline in PLCB-to-FLEX DOSE will be taken from baseline in the double-blind treatment phase.

An overall summary based on all post-baseline visits will include the number and percentage of subjects who have each of the following, will be presented for the

double-blind treatment phase and the DSP-5423P treatment period.

- Maximum suicidal ideation after baseline,
- Any Suicidal Ideation after Baseline and no Suicidal Ideation after Baseline,
- Serious Suicidal Ideation after baseline,
- Suicidal behavior after baseline,
- Any Suicidal Behavior after Baseline and No Suicidal Behavior after Baseline,
- Suicidality after Baseline,
- Emergence of any suicidal ideation*: Subjects who had no suicidal ideation at Baseline and subsequently had any type of suicidal ideation during the treatment phase.
- Emergence of serious suicidal ideation*: Subjects who had no serious suicidal ideation (defined as score of 4 or 5 on the suicidal ideation severity rating**) at Baseline and subsequently had serious suicidal ideation during the treatment phase,
- Worsening of suicidal ideation: most severe suicidal ideation post-baseline was more severe than it was at baseline,
- Emergence of suicidal behavior*: Subjects who had no suicidal behavior at Baseline and subsequently had any type of suicidal behavior during the phase,
- Emergence of suicidality*: Subjects who had no suicidality (neither suicidal ideation nor suicidal behavior) at Baseline and subsequently had any type of suicidality (suicidal ideation or suicidal behavior) during the treatment phase.
- Any completed suicide: Subjects who completed suicide during the treatment phase.

* Subjects who have “Y” at baseline will be excluded from denominator in calculation of percentage.

** Regarding “Suicidal Ideation”, in case that “Non-Specific Active Suicidal Thoughts” is “No”, and following 3 items, “Active Suicidal Ideation with Any Methods (Not Plan) without Intent to Act”, “Active Suicidal Ideation with Some Intent to Act, without Specific Plan”, “Active Suicidal Ideation with Specific Plan and Intent” are all null, all of these 3 items will be set to “No”. This is based on a logic which these 3 items supposed to be followed only by a case of “Yes” in “Non-Specific Active Suicidal Thoughts”.

The number and percentage of subjects with suicidal ideation and suicidal behavior

will be summarized by treatment group for all regions and by country for the double-blind treatment phase on the safety population and for the DSP-5423P treatment period on the DSP-5423P dosed population.

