#### **15.3.8.2 Analysis visits, baseline, and post-baseline measures**

All data will be organized and analyzed according to the scheduled timing as outlined in Table 3 to 5 Schedule of Assessments (p10~13) and according to the visit denoted in the CRFs. Unscheduled visits may be used if scheduled visits are not available, and details will be prespecified in the statistical analysis plan before the interim analysis is performed. The baseline data for statistical analyses will be defined as the last non-missing data on or before Day 1. In analysis for the open-label treatment phase and the DSP-5423P treatment period, the baseline data of the subjects in the Placebo group will be defined as the last non-missing data before the beginning of DSP-5423P application. Post-baseline data for statistical analysis will be defined as the non-missing data on or after Day 1 and through 7 days after the date of final

application of the study drug (excluding baseline). The data collected at the discontinuation visit will be mapped to the next scheduled visit of the actual discontinuation date.

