6 DATA HANDLING

6.1 Day 1

Day 1 is defined as the day of the initial application in the double-blind treatment phase. Relative days after Day 1 are calculated as (date of assessment date – date of Day 1) + 1. Relative days prior to Day 1 are calculated as (date of assessment – date of Day 1). The day before Day 1 is Day -1.

Day 1 is also referred as the initial application date of double-blind treatment phase. The day of final application in the double-blind treatment phase will be referred as the final application date of double-blind treatment phase.

6.2 On-treatment Day 1

On-treatment Day 1 is defined as the day of the initial application of DSP-5423P in this study. Relative days after On-treatment Day 1 are calculated as (date of assessment date – date of On-treatment day 1) + 1. Relative days prior to On-treatment Day 1 are calculated as (date of assessment – date of On-treatment Day 1). The day before On-treatment Day 1 is On-treatment Day -1.

On-treatment Day 1 is also referred as the initial application date of DSP-5423P treatment period. The day of final application of DSP-5423P will be referred as the final application date of DSP-5423P treatment period.

Note that "On-treatment day X" is the same as "Day X" in the 40 mg and 80 mg group. For the placebo group however, "On-treatment day 1" is the first day of receiving an active treatment in the open-label treatment phase and "Day 1" is the first day in the double-blind treatment phase. In general, "Day X" is used for analysis for the double-blind treatment phase. "On-treatment day X" is used for analysis for the DSP-5423P treatment period and specifically excluded the double-blind treatment phase data: for subjects in the placebo group.

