Assessment and tests	Relative Day	Analysis Visit
PANSS, CGI-S, DIEPSS, C-SSRS, Skin irritation assessment, Body weight, Vital signs	Day 1 to 11	Week 1
	Day 12 to 25	Week 2
	Day 26 to 39	Week 4
	Day 40 or later	Week 6
12-lead ECG, Pharmacokinetic	Day 1 to 11	Week 1
	Day 12 to 25	Week 2
	Day 26 or later	Week 6
Laboratory test	Day 1 to 25	Week 2
	Day 26 or later	Week 6

If more than one unscheduled visits satisfy the condition, the earliest one

Statistical Analysis Plan

Version: 2

Study No. D4904020

will be mapped to the analysis visit

Note: non-missing analysis visits will not be replaced.

B. DSP-5423P treatment period

(i) On-Treatment Baseline analysis visit

(1) 40 and 80 mg group in the double-blind treatment phase

Same as the Baseline analysis visit for the double-blind treatment phase.

(2) Placebo group in the double-blind treatment phase

Defined as the last non-missing data in the double-blind treatment phase including unscheduled visits assessed on or before the On-treatment Day 1.

(ii) Post-baseline data

(1) 40 and 80 mg group in the double-blind treatment phase

Defined as the non-missing data on 'On-treatment Day 1' through 7 days after the final application of DSP-5423P, except for Screening and Day 1 (Baseline) visit.

(2) Placebo group in the double-blind treatment phase

Defined as the non-missing data on a day after 'On-treatment Day 1' through 7 days after the final application of DSP-5423P.

(iii) Post-baseline analysis visit for the 40 and 80 mg group

The post-baseline data will be mapped to post-baseline analysis visits, ie, On-treatment Week 1, 2, 4, 6, 7, 8, 10, 14, 18, 22, 26, 30, 34, 42, 50, and 58 according to the CRF visits as follows. Unscheduled visits of the open-label treatment phase will not be mapped.

(1) Scheduled visits except for the discontinuation visits will be mapped regardless of the actual day of assessment as follows:

CRF Visits	DB W1	DB W2	DB W4	DB W6
Analysis Visits	OnT W1	OnT W2	OnT W4	OnT W6
CRF Visits	OL W1	OL W2	OL W4	OL W8
Analysis Visits	OnT W7	OnT W8	OnT W10	OnT W14
CRF Visits	OL W12	OL W16	OL W20	OL W24
Analysis Visits	OnT W18	OnT W22	OnT W26	OnT W30
CRF Visits	OL W28	OL W36	OL W44	OL W52
Analysis Visits	OnT W34	OnT W42	OnT W50	OnT W58

DB, double-blind; OL, open-label; OnT, on treatment; W, Week

Statistical Analysis Plan

Version: 2

Study No. D4904020

- (2) Discontinuation visits will be mapped to the earliest missing analysis visit based on the relative day of assessment as follows:

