7.7.1 Adverse Events

Treatment emergent AEs (TEAEs) are defined as follows:

- TEAEs (the double-blind treatment phase): Events with start date on or after the date of initial application of study drug in the double-blind treatment phase, and up to 17 days after the date of final application of study drug in the double-blind treatment phase and before the first application of DSP-5423P in the open-label treatment phase.
- TEAEs (DSP-5423P treatment period): Events with start date on or after the date of initial application of DSP-5423P either in the double-blind treatment period for 40MG and 80MG groups or in the open-label treatment period for placebo group and up to 17 days after the date of final application date of DSP-5423P.

AE with missing or incomplete start date after imputation will be considered as TEAE.

Treatment-related TEAE:

A treatment-related TEAE is defined as a TEAE for which the causal relationship to the study treatment is either 'definite', 'probable', or 'possible'.

Common TEAE:

Common TEAE in the double-blind treatment phase are PT of TEAEs experienced by 2% or more subjects in 40MG or 80MG group in the safety population.

Common TEAE in the DSP-5423P treatment period are PT of TEAEs experienced by 2% or more subjects in the overall-to-FLEX DOSE group in the DSP-5423P dosed population.

The summary of AEs will be limited to treatment-emergent AEs (TEAEs). The number and percentage of subjects with TEAEs during the double-blind treatment phase on the safety population and DSP-5423P treatment period on the DSP-5423P dosed population will be summarized by preferred term, system organ class, and treatment group. Summaries will be repeated by country and race.

Specifically, this will cover the following items:

- any TEAE;
- TEAE leading to death;
- TEAE leading to treatment discontinuation;
- serious TEAE;

- extrapyramidal TEAE;
- skin-related TEAE;
- treatment-related TEAE;
- treatment-related TEAE leading to death;
- treatment-related TEAE leading to treatment discontinuation;
- treatment-related serious TEAE;
- treatment-related extrapyramidal TEAE;
- treatment-related skin-related TEAE;

Skin-related TEAE is defined as the TEAE occurred at the application site (recoded in the CRF) and identified as TEAE with a wording “Application site” in MedDRA LLT.

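### The C-SSRS baseline for placebo-origin subjects in the DSP-5423P period is taken from before the double-blind phase, against the Protocol and the SAP's own general rule

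*SAP*

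**What the plan says.** Two rules in the plan define the reference point for subjects who move from placebo to open-label DSP-5423P.

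- **General rule.** For analyses of the open-label phase and the DSP-5423P treatment period, Protocol 15.3.8.2 states that "the baseline data of the subjects in the Placebo group will be defined as the last non-missing data before the beginning of DSP-5423P" is applied. SAP 6.3 B(i)(2) carries this out for the placebo group: "Defined as the last non-missing data in the double-blind treatment phase including unscheduled visits assessed on or before the On-treatment Day 1". Post-baseline data for the same subjects, in 6.3 B(ii)(2), are "Defined as the non-missing data on a day after 'On-treatment Day 1' through 7 days after the final application of DSP-5423P". SAP 6.2 adds that analyses of this period "specifically excluded the double-blind treatment phase data: for subjects in the placebo group". The visit mapping for the placebo group in 6.3 B lists C-SSRS by name, and no exception is stated.
- **C-SSRS rule.** SAP 7.7.3 ends its paragraph on the by-visit table with: "Note that for the DSP-5423P treatment period summary, baseline in PLCB-to-FLEX DOSE will be taken from baseline in the double-blind treatment phase". SAP 6.3 A(i) defines that baseline as the last Screening or Day 1 value.

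The next paragraph of 7.7.3 introduces a second table: "An overall summary based on all post-baseline visits will include the number and percentage of subjects who have each of the following". It holds the emergence and worsening rows and is also produced for the DSP-5423P period. Its rows refer to baseline without saying which one. A footnote to the emergence rows says that subjects already positive "at baseline will be excluded from denominator in calculation of percentage".

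SAP section 8, on changes in planned analyses, is marked not applicable.

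**The concern.** The C-SSRS sentence contradicts the Protocol and SAP 6.3 without explanation. For the same period, PANSS and CGI-S (SAP 7.6.2.1.3) and DIEPSS (7.7.2) are measured from the last evaluation before DSP-5423P. Treatment-emergent adverse events (7.7.1) start from the first DSP-5423P application, "either in the double-blind treatment period for 40MG and 80MG groups or in the open-label treatment period for placebo group". Only C-SSRS reaches back across six weeks of placebo.

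The scope of the sentence is also unclear. If it extends to the emergence rows, a positive rating that first appeared on placebo can be reported as emergent on DSP-5423P. Conversely, suicidality that had cleared before DSP-5423P and returned on it can vanish from those rows. C-SSRS is a listed safety endpoint and long-term safety is a secondary objective, so a wrong label matters even where numbers are small.

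**Working it through.** The plan gives no figure to reproduce. The check compares the two rules, then counts where they disagree.

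**1. Age of the baseline.** Protocol Table 3 schedules C-SSRS first at Visit 2 (Day -2 to 1), not at Screening, and again at Visit 6 (Day 40 to 43) before open-label dosing. There is no Day 0.

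- Shortest gap: Day 1 to Day 40 = 39 days.
- Longest gap: Day -2 to Day 43 = 2 + 42 = 44 days.

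Protocol 8.3.1 requires all scheduled Visit 6 assessments for open-label entry, so entrants should have the later rating. Weeks 1, 2 and 4 serve neither as baseline (normally) nor as post-baseline data under either rule. The choice is therefore normally between Visit 2 and Week 6.

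**2. Emergence rows, if the sentence covers them.** Code each subject 0 (absent) or 1 (present) at Visit 2, Week 6 and any open-label rating. Entries are contributions to numerator/denominator.

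| Visit 2, Week 6, open label | SAP 7.7.3 sentence | SAP 6.3 B | Difference |
|---|---|---|---|
| 0,0,0 | 0/1 | 0/1 | none |
| 0,0,1 | 1/1 | 1/1 | none |
| 0,1,0 | 0/1 | 0/0 | denominator only |
| 0,1,1 (pattern a) | 1/1 | 0/0 | numerator and denominator |
| 1,0,0 | 0/0 | 0/1 | denominator only |
| 1,0,1 (pattern b) | 0/0 | 1/1 | numerator and denominator |
| 1,1,0 | 0/0 | 0/0 | none |
| 1,1,1 | 0/0 | 0/0 | none |

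Four of the eight patterns differ, two of them in the numerator, in opposite directions. Suicidality that arose on placebo, was absent at Week 6 and recurred in open label (0,0,1) is emergent under both rules.

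**3. Worsening row.** With ideation severity 0 to 5 and open-label maximum M, the rules differ only when min(Visit 2, Week 6) < M ≤ max(Visit 2, Week 6). Of 6 × 6 × 6 = 216 combinations, 35 count as worse only under the 7.7.3 sentence and 35 only under 6.3 B. These are logical patterns, not expected frequencies.

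**4. Possible size.** The documents give no C-SSRS rates, so this step rests on assumptions.

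- Placebo subjects: SAP Appendix II lists 582 randomized; at 1:1:1, 582/3 = 194.
- Entry to open label assumed 60 to 75%: 194 × 0.60 = 116; 194 × 0.75 = 146.
- Pattern (a) assumed in 0 to 3% of entrants: 0 up to 116.4 × 0.03 = 3.5 or 145.5 × 0.03 = 4.4 subjects. The same range holds for pattern (b).
- Net (a minus b): about -4 to +4.
- Shift per pattern (a) subject in PLCB-to-FLEX DOSE, with k other emergent subjects and n in the denominator: (k+1)/n - k/(n-1). At k = 0, n = 116: 1/116 = 0.86 points. At k = 6, n = 146: 7/146 - 6/145 = 0.66 points. Pattern (b) shifts it by about the same amount the other way.
- A denominator-only subject, at most (k = 6, n = 116): 6/115 - 6/116 = 0.045 points.
- Overall-to-FLEX DOSE, with all 2 × 194 = 388 active-arm subjects dosed and denominator exclusions ignored: 1/(388 + 146) = 0.19 to 1/(388 + 116) = 0.20 points per subject.

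**The case against.** The strongest reply is that the sentence closes the by-visit paragraph and the emergence rows belong to a different table in the next one. Read by position, it fixes only the by-visit baseline row, the general rule governs the rest, and nobody is misclassified. A C-SSRS-specific instruction would also ordinarily override a general one, so the by-visit row itself is not ambiguous to a programmer.

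Both points have force, and the emergence consequence is conditional for that reason. They do not clear the text. Precedence within the SAP does not settle the departure from Protocol 15.3.8.2, which is neither explained nor recorded. The sentence speaks of the summary for the whole period, and 7.7.3 defines no other baseline for the emergence rows, so the wider reading is reasonable. On the narrow reading, the by-visit baseline row and the emergence denominators use different ratings for the same subjects and need not reconcile.

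Other reservations stand:

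- No recall period is stated in Protocol 11.3.3 or SAP 6.8.4, so a positive Week 6 rating is a recorded status and does not prove ideation on that day.
- SAP 6.3 B says on or before On-treatment Day 1, slightly wider than the Protocol. The Visit 6 rating must precede dosing, so this matters only for an unscheduled rating that day.
- Adverse events are classed by onset date and C-SSRS by visit rating. A disagreement between the two tables would be an inconsistency of presentation, not a logical contradiction.
- The Protocol asks only for counts of ideation and behavior; the emergence and worsening rows are SAP additions. The any and maximum rows and the post-baseline by-visit counts do not depend on the baseline. The double-blind summary and the listings allow either classification to be rebuilt.

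**Conclusion.** The concern holds. The C-SSRS sentence in SAP 7.7.3 conflicts with Protocol 15.3.8.2 and SAP 6.3 B(i)(2), and this is certain from the text. On the narrow reading the damage is one descriptive baseline row that shows a rating about six weeks too old. On the wider reading, pattern (a) subjects are wrongly classed as emergent on DSP-5423P and pattern (b) subjects are wrongly left out.

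Under the assumed entry and pattern rates, that is 0 to about 4 subjects each way, with unknown net direction. Each would move the PLCB-to-FLEX DOSE percentage by about 0.7 to 0.9 points and the Overall-to-FLEX DOSE percentage by about 0.2. Three provisions push toward the low end: screening exclusion 6, the safety condition at open-label entry, and suicide ideation as a listed reason for termination. Only placebo-origin subjects, and the overall column through them, are affected. The primary analysis is not.

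**What to change.** Delete the baseline sentence in SAP 7.7.3. Use the on-treatment baseline of SAP 6.3 B(i)(2), normally Visit 6, for PLCB-to-FLEX DOSE in every C-SSRS summary of the DSP-5423P treatment period: the by-visit baseline row, the emergence and worsening rows, and the emergence denominators.

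If the double-blind baseline is wanted as a deliberate C-SSRS exception, present it as a labelled supplementary summary, state which rows it covers, and record the departure from Protocol 15.3.8.2 in SAP section 8.

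The cost is one sentence, plus one line in section 8 if the supplement is kept. No new data are needed, because C-SSRS is already scheduled at Visit 6 before open-label dosing.

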7.7.4 Skin Irritation Assessment

Skin irritation will be summarized by counts and percentage in each category for the double-blind treatment phase on the safety population and DSP-5423P treatment period on the DSP-5423P dosed population: Negative, Faint erythema, Erythema, Erythema and Edema, Erythema + Edema + Papules, Serous papules, Vesicles and Coalescing vesicles. Maximum severity based on all post-baseline visits up to and including LOCF endpoint will be also summarized as well as other visits. Summaries will be repeated by country.

7.7.5 Laboratory Evaluations

Data for the following hematology, blood chemistry, and urinalysis parameters received from the central laboratory will be listed and summarized by treatment group and visit including LOCF endpoints for the double-blind treatment phase using the safety population and for the DSP-5423P treatment period on the DSP-5423P dosed population. Observed values and changes from baseline will be summarized.

Statistical Analysis Plan

Version: 2

Study No. D4904020

Hematology	Blood Chemistry	Urinalysis
1. white blood cell count,	1. total protein,	1. glucose,
2. red blood cell count,	2. total bilirubin,	2. protein,
3. hemoglobin,	3. AST,	3. occult blood,
4. hematocrit,	4. ALT,	4. urobilinogen
5. platelet count,	5. ALP,	
6. neutrophils,	6. γ -GTP,	
7. eosinophils,	7. LDH,	
8. basophils,	8. total cholesterol,	
9. monocytes,	9. triglycerides,	
10. lymphocytes	10. BUN,	
	11. creatinine,	
	12. CK,	
	13. Na,	
	14. K,	
	15. Cl,	
	16. blood glucose,	
	17. HbA1c,	
	18. serum prolactin	

All laboratory data will be reported in conventional units. Out-of-reference-range values will be flagged as high (H) or low (L) in the listings.

For analysis purposes, values preceded by a “<” sign (i.e. those below the limits of quantification) will be set as missing. If values preceded by a “>” sign (i.e., those above the limits of quantification) are observed, handling will be discussed at BDRM. Note that these values with a “<” or “>” sign will be presented values as reported from the laboratory in the listing.

Mean change from baseline to Week 6 (LOCF) in selected parameters, which are serum prolactin concentration, glucose and HbA1c, will be analyzed using a nonparametric rank ANCOVA. For each pairwise comparison versus placebo, values of the change from baseline at LOCF endpoint and baseline values will be ranked. A linear regression will be conducted on the ranked change from baseline with ranked baseline value as independent variable to produce regression residuals. Using the values of the residuals as scores, Mantel-Haenszel row mean score tests will be produced for each DSP-5423P group versus placebo (Stokes, Davis, & Koch, 1995).

```
* compute the ranks of the response variable and covariate;
proc rank data = &ads out=ranks npuls12 ties=mean;
  var chg base;
  ranks rkchg rkbases;
```

Statistical Analysis Plan

Version: 2

Study No. D4904020

```
run;
* calculate the residuals from the linear regression;
proc glm data=ranks;
  model rkchg=rkbase;
  output out=residual r=resid;
run;
* CMH mean score statistics are used to compare the groups;
proc freq data=residual;
  tables trt01p*resid / cmh2;
  ods output diffs=diff;
run;
```

Markedly Abnormal Post-Baseline Laboratory Values (MAPLV) for selected laboratory parameters can be found in Table 1. The criterion of MAPLV is satisfied if a value falls into the markedly abnormal range. Subjects will be represented in the count of a particular MAPLV if they have experienced that MAPLV at least once in the post-baseline (including unscheduled visits), regardless of baseline value, up to and including LOCF endpoints and repeat for each country. Only parameters with MAPLV throughout the study period per subject will be listed.

Table 1 Criteria for Markedly Abnormal Post-Baseline Laboratory Values

Hematology Parameter	Markedly Abnormal Range
Hemoglobin	Male: ≤ 11.5 g/dL
	Female: ≤ 9.5 g/dL
Hematocrit	Male: $\leq 37\%$
	Female: $\leq 32\%$
WBC	$\leq 2.8 \times 10^3/uL$
	$\geq 16 \times 10^3/uL$
Platelets	$\leq 75 \times 10^3/uL$
	$\geq 700 \times 10^3/uL$
Chemistry Parameter	Markedly Abnormal Range
ALT	$\geq 3 \times ULN$
AST	$\geq 3 \times ULN$
Alkaline Phosphatase	$\geq 1.5 \times ULN$
Na/Sodium	< 130 mEq/L
	> 150 mEq/L
K/Potassium	< 3 mEq/L
	> 5.5 mEq/L
Cl/Chloride	< 90 mEq/L
	> 115 mEq/L

Statistical Analysis Plan

Version: 2

Study No. D4904020

Blood Glucose (fasting)	< 50 mg/dL > 250 mg/dL
HbA1c	≥ 7.5%
Total Bilirubin	> 2 x ULN
Blood Urea Nitrogen	> 30 mg/dL
Creatinine	> 2.0 mg/dL
CK	> 3 x ULN
Serum Prolactin	≥ 5 x ULN
Triglycerides (fasting)	> 300 mg/dL
Total Cholesterol (fasting)	> 300 mg/dL

Box plot of observed value of the hematology and blood chemistry parameters will be provided for the double-blind treatment phase and the DSP-5423P treatment period by the treatment group and visit.

